9.4.1. Primary Analyses

9.4.1.1. Dose Response Model

The primary endpoint is change in Hgb from baseline at Day 29. To model the dose-response relationship a three-parameter Emax model is planned, where Emax is assumed an appropriate model based on the biology and QD-dose-response modeling completed to date for GSK 1278863.

This model assumes the following form:

$$\Delta Hgb = E0 + \frac{(Emax - E0)}{1 + (\frac{ED50}{dose})} + \in$$

Where:

- \bullet AHgb is the change in Hgb from baseline at Day 29
- E0 is the placebo response
- Emax is the maximum response
- ED50 is the dose that attains the intermediate response, i.e. where (E0+Emax) / 2, is attained

• ε is a random error assumed to be normally distributed with mean zero and constant variance (σ^2)

The observed change in Hgb from baseline at Day 29 will be used as the response variable in the Emax model. Subjects who have a Day 15 Hgb measurement but a missing Day 29 Hgb measurement will be included with a Day 29 value imputed (see Section 9.3.2). Any subject who prematurely discontinues dosing prior to Day 15 will be non-evaluable for the dose-response analysis.

The Emax model will be fitted using Bayesian statistical methods (i.e. a posterior Emax model). Prior distributions for the model parameters have been based on the estimates obtained from GSK study PHI113633. This modeling provides confidence in setting prior distributions for E0, however, there is greater uncertainty in the estimation of Emax and ED50 and this will be explored in sensitivity analyses that will apply alternative (weaker) prior distributions.

Table 6 Prior Distributions for the Primary Model

Emax Model Parameters	Bayesian Priors
E0	~Normal (-0.67, (0.146) ²)
Emax	~Normal (5.26, (1.337) ²)
ED50	~Uniform (10, 120)
Tau (1/σ²)	~Gamma (1,1)

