
Prior Distributions of the Primary Model
 
  
 Emax Model Parameters	Bayesian Priors	
   
 E0	~Normal (-0.67, (0.146)²)	
 
 Emax	~Normal (5.26, (1.337)²)	
 
 ED50	~Uniform (10, 120)	
 
 Tau (1/σ^2)	~Gamma (1,1)	
  
		Emax Model Parameters	Bayesian Priors	E0	~Normal (-0.67, (0.146) ²)	Emax	~Normal (5.26, (1.337) ²)	ED50	~Uniform (10, 120)	Tau (1/ σ^2)	~Gamma (1,1)
Emax Model Parameters	Bayesian Priors										
E0	~Normal (-0.67, (0.146) ²)										
Emax	~Normal (5.26, (1.337) ²)										
ED50	~Uniform (10, 120)										
Tau (1/ σ^2)	~Gamma (1,1)										
Model Fitting in SAS											

The model will be fitted in SAS using the MCMC procedure.
 
 Blocking: Sampling blocks of parameters instead of the parameters separately may speed up the convergence to the target distribution. Blocks are specified in the PARMS statement. Seed: The seed for reproducibility of results will be set to 123. 											
Starting Values											

In order to check the validity of the Emax model fit, five separate Monte Carlo Markov Chain's chains will be fitted each with the following starting points:
 
 Chain 1) E0 = -1.2, Emax = 5.5, ED₅₀ = 50, var = 1 Chain 2) E0 = -0.75, Emax = 7, ED₅₀ = 22.5, var = 2 Chain 3) E0 = -1.65, Emax = 4, ED₅₀ = 80, var = 0.5 											

Primary Statistical Analyses
 
 ▪ Chain 4) $E_0 = -1.65$, $E_{max} = 7$, $ED_{50} = 22.5$, $var = 1$ ▪ Chain 5) $E_0 = -0.75$, $E_{max} = 4$, $ED_{50} = 100$, $var = 2$ 
When the starting values are taken in an area where the posterior probability is low, it may take a long time to escape from the starting positions and mixing could be low initially. In this case, other starting values could be tried.

Burn In
 
“Burn-in” is the portion of the chain where convergence has not yet been achieved. “Discarding burn-in” is the practice of discarding the initial portion of a Markov chain. This will be set to 5000 iterations.

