
Dose ratio between TIW and QD doses that produce the same Hgb response will be estimated by different approaches. The dose ratio that will be used to make an informative decision about conversion of QD initial and maintenance dose regimens to three-times weekly doses/regimens will be based on the totality of the data obtained from different approaches.
 
 The TIW dose response estimations will be obtained from the above fitted models. In addition, the QD dose response estimations will also be obtained by fitting the same models as described above (two Emax models and a linear model) using GSK study PHI113633 data excluding Japan. The prior information and the starting values for the QD Bayesian Emax model is shown below: 
Five separate Monte Carlo Markov Chain's chains will be fitted each with the following starting points:
 
 Chain 1) $E0 = -1.2, Emax = 5.5, ED_{50} = 16, var = 1$ Chain 2) $E0 = -0.75, Emax = 7, ED_{50} = 22.5, var = 2$ Chain 3) $E0 = -1.65, Emax = 4, ED_{50} = 9.5, var = 0.5$ Chain 4) $E0 = -1.65, Emax = 7, ED_{50} = 22.5, var = 1$ Chain 5) $E0 = -0.75, Emax = 4, ED_{50} = 9.5, var = 2$ 
Prior Distributions for QD Bayesian Emax Model
 
  
 Emax Model Parameters	Bayesian Priors	
   
 E0	$\sim \text{Normal}(-1.2, (0.45)^2)$	
 
 Emax	$\sim \text{Normal}(5.5, (1.5)^2)$	
 
 ED50	$\sim \text{Uniform}(5, 50)$	
 
 Tau ($1/\sigma^2$)	$\sim \text{Gamma}(1, 1)$	
  
		Emax Model Parameters	Bayesian Priors	E0	$\sim \text{Normal}(-1.2, (0.45)^2)$	Emax	$\sim \text{Normal}(5.5, (1.5)^2)$	ED50	$\sim \text{Uniform}(5, 50)$	Tau ($1/\sigma^2$)	$\sim \text{Gamma}(1, 1)$
Emax Model Parameters	Bayesian Priors										
E0	$\sim \text{Normal}(-1.2, (0.45)^2)$										
Emax	$\sim \text{Normal}(5.5, (1.5)^2)$										
ED50	$\sim \text{Uniform}(5, 50)$										
Tau ($1/\sigma^2$)	$\sim \text{Gamma}(1, 1)$										

Primary Statistical Analyses

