- For each TIW dose (10mg, 15mg, 25mg, and 30mg), the observed mean Hgb response (Hgb change from baseline) at day 29 can be calculated. Using the observed mean Hgb response values as a bridge, the corresponding QD doses will be estimated using Emax models or a linear model. TIW dose divided by the corresponding QD dose will be used to estimate the dose ratio between them. The TIW doses, the observed mean Hgb responses, and the corresponding estimated QD doses, dose ratios, and the 95% CIs (bootstrap CIs or Bayesian credibility intervals) will be displayed in a table.
- Another way to estimate the dose ratios is to use a selected series of Hgb responses. For each Hgb response value (such as a change of 0.25 g/dL), the corresponding TIW dose and QD dose can be calculated using either an Emax model, or a linear model. The possible Hgb responses choices are: a change of -0.5, -0.25, 0, 0.25, 0.5, 0.75, 1 g/dL between baseline and day 29. The Hgb responses, and the corresponding TIW doses, QD doses, Dose ratios, and their 95% CIs (bootstrap CIs or Bayesian credibility intervals) will be presented in a table.
- In the above two methods, fairly similar dose ratios across the doses indicate the dose ratios is not dose-dependent. Under this assumption, the ratio between the estimated ED50s from the TIW Emax model (this study) and the QD Emax model (GSK study PHI113633) would be equivalent to the dose ratio, as well as the ratio between the estimated slopes from the QD linear model (GSK study PHI113633) and three-times weekly linear model (this study).
- An additional way to explore the dose ratio is to draw a TIW dose vs. QD dose plot using the pair of TIW doses and QD doses obtained from the above methods. The appropriate models to investigate the dose ratio will be fitted based on the plot. If the relationship between the TIW doses and the QD doses is linear, then a linear model $Dose_{TIW} = a + bDose_{QD}$ can be fitted. If the relationship between the TIW and QD doses is generally linear and the magnitude of a dose not deviate from zero in a clinically meaningful way, then it suggests that the dose ratio is not dose dependent. Otherwise if a shows a clinically meaningful difference from 0 or the relationship between the TIW and QD doses is not linear, then it suggests that the dose ratio may be dose dependent. Additional models may be used to further examine how the dose ratio changes when QD dose changes.

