- The primary dose-response model will be fitted based on the completer population. A table summarizing the results of these dose response analyses along with the dose response curve (alongside the primary analysis curve) will be produced on this population.
- The primary dose-response analysis will be repeated using the PP population if it comprises $\leq 80\%$ of the ITT population. A table summarizing the results of these dose response analyses along with the dose response curve (alongside the primary analysis curve) will be produced on this population.
- The dose-response Emax model will be fitted using alternative (weaker, less informative) prior distributions for the Emax model parameters. The results from this sensitivity prior analysis will be tabulated as previously described for the primary dose-response model.

Alternative Prior Distributions

Emax Model Parameters	Bayesian Priors
E0	\sim Normal (-1.2, $(1)^2$)
Emax	\sim Normal (5, $(3)^2$)
ED50	\sim Uniform (2, 200)
Tau ($1/\sigma^2$)	\sim Gamma (1,1)

- A 3-parameter frequentist Emax model will be fitted based on ITT population. It will be fitted using PROC NLMIXED or PROC NLIN, and will be presented as described above.
- A linear model will be fitted to the dose-response data based on ITT population, if a linear relationship looks plausible across the three-times weekly dose range and will be presented as described above. This analysis will be repeated in the Completers and Per Protocol populations.

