2.16.	ITT	Dose_Ratio_2	Summary of Dose Ratio Between Three-Times Weekly Doses (Estimated by Bayesian Emax Model) and QD Doses (Estimated by Linear Model) at Selected Hgb Responses	Will be performed by GSK when the dose-response models are appropriate
2.17.	ITT	Dose_Ratio_2	Summary of Dose Ratio Between Three-Times Weekly Doses (Estimated by Frequentist Emax Model) and QD Doses (Estimated by Bayesian Emax Model) at Selected Hgb Responses	Will be performed by GSK when the dose-response models are appropriate
2.18.	ITT	Dose_Ratio_2	Summary of Dose Ratio Between Three-Times Weekly Doses (Estimated Frequentist Emax Model) and QD Doses (Estimated by Frequentist Emax Model) at Selected Hgb Responses	Will be performed by GSK when the dose-response models are appropriate
2.19.	ITT	Dose_Ratio_2	Summary of Dose Ratio Between Three-Times Weekly Doses (Estimated by Frequentist Emax Model) and QD Doses (Estimated by Linear Model) at Selected Hgb Responses	Will be performed by GSK when the dose-response models are appropriate
2.20.	ITT	Dose_Ratio_2	Summary of Dose Ratio Between Three-Times Weekly Doses (Estimated by Linear Model) and QD Doses (Estimated by Bayesian Emax Model) at Selected Hgb Responses	Will be performed by GSK when the dose-response models are appropriate

Efficacy: Tables				
No.	Population	IDSL / TST ID / Example Shell	Title	Programming Notes
2.21.	ITT	Dose_Ratio_2	Summary of Dose Ratio Between Three-Times Weekly Doses (Estimated by Linear Model) and QD Doses (Estimated by Frequentist Emax Model) at Selected Hgb Responses	Will be performed by GSK when the dose-response models are appropriate
2.22.	ITT	Dose_Ratio_2	Summary of Dose Ratio Between Three-Times Weekly Doses (Estimated Linear Model) and QD Doses (Estimated by Linear Model) at Selected Hgb Responses	Will be performed by GSK when the dose-response models are appropriate
2.23.	ITT	Model_ratio	Summary of Dose Ratio between Three-Times Weekly Dose and QD Dose Estimated by Emax Model and Linear Model	Will be performed by GSK
2.24.	ITT	Linear_TQ	Linear Model between the corresponding QD and TIW doses with the same Change in Hemoglobin at Day 29	Will be performed by GSK
2.25.	ITT (PHI113633)	Emax633	Summary of Posterior Estimates from the Bayesian 3 Parameter Emax Dose-Response Model and the Estimates from the Frequentist 3 Parameter Emax Dose-Response Model for Change in Hemoglobin at Week 4 (Based on PHI113633 data excluding Japan)	Will be performed by GSK

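### At the PHI113633 ED50 estimate, the SAP's ED50 prior bounds pull the Bayesian ED50 ratio toward about 2.4 to 2.8, so it should not count as a dose-ratio estimate

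*SAP*

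**What the plan says.** SAP 7.1.2 (Dose Ratio Estimation) plans several routes to the TIW:QD dose ratio:

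- TIW dose against the QD dose that reproduces the observed mean Hgb response.
- TIW and QD doses that give the same selected Hgb change (Tables 2.14 to 2.22).
- A regression of matched TIW doses on QD doses.
- The ratios of ED50s and of linear slopes.

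The last route carries a condition: "fairly similar dose ratios across the doses indicate the dose ratios is not dose-dependent. Under this assumption". Only on that footing does the SAP offer an equivalent of the dose ratio: "the ratio between the estimated ED50s from the TIW Emax model (this study) and the QD Emax model (GSK study PHI113633) would be equivalent". The slopes are treated likewise. Protocol 9.4.1.2 carries the same condition. The conversion decision rests on all approaches taken together.

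The two Bayesian Emax models are fitted separately with different priors. For TIW, ED50 is uniform on 10 to 120 mg, E0 is normal with mean -0.67 and SD 0.146, and Emax is normal with mean 5.26 and SD 1.337. For QD, ED50 is uniform on 5 to 50 mg, E0 is normal (-1.2, SD 0.45) and Emax is normal (5.5, SD 1.5). SAP 11.14.6 lists Table 2.23, "Summary of Dose Ratio between Three-Times Weekly Dose and QD Dose Estimated by Emax Model and Linear Model". A weaker TIW prior set (ED50 uniform on 2 to 200 mg) is planned, and "The results from this sensitivity prior analysis will be tabulated as previously described for the primary dose-response model". No weaker set is given for the QD model, and none of Tables 2.11 to 2.23 is titled as using one.

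**The concern.** Doses reach 30 mg TIW and 12 mg QD, while the ED50s used for Protocol Table 4 are 33.41 mg QD and 78 mg TIW. When an ED50 lies that far out, a bounded uniform prior is not neutral. Here the two sets of bounds are scaled to each other by almost exactly the ratio the trial is meant to estimate. The SAP warns that ED50 will be poorly estimated, which is a warning of imprecision. It does not warn of a pull toward one value.

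The stake is the conversion from QD to TIW regimens. If the true ratio were 3 or 4, this estimate would tend to sit nearer 2.33 than it should, alongside other estimates that do not. The SAP has no rule for which to discount.

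**Working it through.** **Inputs.** E0 = -0.666, Emax = 5.258, SD 1 g/dL, and QD ED50 of 33.41 mg (estimated) or 16 mg (assumed when PHI113633 was planned), all from Protocol 9.2.1. TIW doses 0, 10, 15, 25 and 30 mg with 15 evaluable per arm (Protocol 4.2, 4.3). QD range 4 to 12 mg (Protocol 4.4). Priors from SAP 7.1.2. *Assumption:* PHI113633 arm sizes are not stated. I used 39 on placebo and about 35 at each of 4, 6, 8, 10 and 12 mg, guided by the mock column totals in SAP 11.14.3, and varied this from 20 to 100 per arm.

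**1. Reproduce Protocol Table 4.** The dose giving response x is D = ED50 (x - E0)/(Emax - x). The half-width is 1.96 x SE(D) by the delta method.

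- Target dose: 2.85 and 5.93 (Table 4: 2.86 and 5.94).
- MED: 2.84 and 5.33 (Table 4: 2.85 and 5.34).

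The model and inputs therefore match the sponsor's.

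**2. What the bounds imply before any data.** Upper limits: 120/50 = 2.40. Prior means: 65/27.5 = 2.36. The median of the ratio of the two uniforms is also 2.36. With QD ED50 = 33.41, a true ratio of 3 puts the TIW ED50 at 100.2 mg (inside). A ratio of 4 puts it at 133.6 mg (outside). The limit is crossed at 120/33.41 = 3.59.

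**3. Why the data do not correct this.** Take a true TIW ED50 of 133.64 mg, with Emax - E0 = 5.924. The effect over placebo at 30 mg is 5.924 x 30/163.64 = 1.086. An ED50 of 90 mg matches it with Emax - E0 = 1.086 x 120/30 = 4.344. That is Emax = 3.68, or (5.26 - 3.68)/1.337 = 1.2 prior SDs below centre. At 10, 15 and 25 mg the two curves differ by 0.022, 0.023 and 0.011 g/dL. The standard error of an arm mean is 1/√15 = 0.26. The trial cannot tell the two apart, yet the implied ED50 ratios are 4 and 90/33.41 = 2.69. Because the curves agree over the studied doses, ratios read off at a given response are much less affected.

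**4. Simulation under a truly constant ratio.** ED50 posteriors were computed on a grid with E0 and Emax integrated out, and the ratio was formed from independent TIW and QD draws. A range in a cell spans repeated runs with slightly different settings. ED50-ratio entries are means of posterior medians; the last two columns are medians over trials.

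| True ratio | ED50 ratio, SAP bounds | Mean 95% interval | ED50 ratio, bounds 10–400 / 5–150 | Response-matched | Linear slopes |
|---|---|---|---|---|---|
| 2.33 | 2.38–2.40 | 1.03–5.69 | 2.45 | 2.25–2.33 | 2.38 |
| 3 | 2.66–2.69 | 1.24–6.18 | 3.18–3.28 | 2.85–2.89 | 2.76–2.89 |
| 4 | 2.80–2.84 | 1.41–6.54 | 4.48–4.53 | 3.61–3.64 | 3.47–3.65 |

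Under the SAP bounds the interval covered the truth in 100% of trials, and it contained 2.33 in 100% of trials when the truth was 3 or 4. Widening the bounds alone removes the compression, so the bounds are the cause. The response-matched intervals covered in 95 to 99% of trials. At a true ratio of 4 and zero Hgb change they excluded 2.33 in 57%.

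**5. Sensitivity (true 3 / true 4).**

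- QD arms of 20 to 100: 2.63–2.79 / 2.83–2.89, coverage 99.6 to 100%.
- TIW arms of 100: 2.74 / 2.90.
- QD ED50 of 40, 30, 25, 20 and 16 mg: 2.56/2.67, 2.77/2.99, 2.92/3.34, 3.03/3.78 and 3.14/4.09.
- The SAP's weaker TIW priors with the QD priors unchanged: 3.43–3.45 / 3.74–3.77, but 2.99 when the truth is 2.33. Loosening one model only moves the bias.

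**The case against.** The case for leaving the plan alone is substantial. The equivalence is stated conditionally, and it is mathematically right for the true curves: a ratio constant over the whole curve implies common E0 and Emax. Both documents say the ED50s are poorly estimated and prefer the linear model where it fits. No hypothesis is tested, and this is one estimate among several. An interval of roughly 1 to 6 announces its own lack of information. The prior and posterior ED50 density plots (Figure 2.12) and the weaker-prior and frequentist estimates in Table 2.5 would show prior dominance on the TIW side. The Table 2.23 shell is not in the text available, so its exact rows and intervals are inferred from its title and from SAP 7.1.2.

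Most of this stands, and it limits the point to one estimate. It does not remove it. The simulations have a constant ratio, so the SAP's condition is met in truth and the compression remains. The caveat does not tell a reader which way the estimate leans, and no planned dose-ratio table is identified as using the weaker priors.

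A reader might infer that the estimate can never exceed 2.8. It can: at true ratios of 3 and 4, about 12 to 14% and 13 to 22% of trials reached 3 or more, and the bounds themselves permit up to 120/5 = 24. A reader might also infer that the whole plan would report about 2.33 whatever the truth. The response-matched and slope columns above contradict that.

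**Conclusion.** The point holds for the Bayesian ED50 ratio alone. At the sponsor's own QD ED50 estimate of 33.41 mg it averages about 2.7 for a true ratio of 3 and 2.8 for a true ratio of 4, with an interval that over-covers and does not separate either from 2.33. The cause is the pair of ED50 bounds. The size depends on the QD ED50: the effect shrinks below about 25 to 30 mg and is gone at 16 mg.

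This rests on assumed PHI113633 arm sizes and an assumed 8 mg arm, a correct Emax model, and the same E0, Emax and SD in both studies. The primary dose-response analysis is not undermined, and the other planned ratio estimates would expose the discrepancy. It is a worthwhile correction to a biased input, not a flaw that invalidates the plan.

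**What to change.** Preferred: state in SAP 7.1.2 that the Bayesian ED50 ratio is not a dose-ratio estimate, omit it from Table 2.23 and from the evidence for conversion, and rely on the response-matched and linear ratios. This is a wording change only.

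If it is kept, widen the ED50 bounds consistently in both the TIW and QD models, add a weaker prior set for the QD fit, and report the Bayesian dose-ratio tables under weaker priors for both studies. The cost is one or two extra PROC MCMC runs and a wider interval (with bounds of 10–400 and 5–150 mg, about 1.24 to 9.28 at a true ratio of 3). Those bounds are illustrative, and they overshoot somewhat at a true ratio of 4.

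A single Emax model for both studies with a ratio parameter is optional. It requires a common E0 and Emax across two separate trials, which is a debatable assumption and is not needed to resolve this point.

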- Although the Emax models and the linear model will be explored to estimate the dose ratio between the TIW and the QD doses, the linear model will be more reliable if it is well-fitted across the TIW and the QD dose range. This is because the QD and TIW dose ranges are expected to only cover the beginning part of the Emax curves. Therefore if any doses lie outside the dose ranges (such as ED50), they will be poorly estimated.
- The 95% bootstrap CI of the estimated dose ratios can be constructed based on the 2.5 percentile and the 97.5 percentile of 1000 bootstrap simulations (Efron and

Primary Statistical Analyses
 
Tibshirani, 1993).
 
 For Bayesian Emax models, the posterior distributions of the estimated doses will be obtained by the PROC MCMC procedure to estimate the dose ratios, of which the 95% Bayesian credibility intervals can be constructed based on the 2.5 percentile and the 97.5 percentile of the 500,000 estimations.

Model Checking & Diagnostics
 
 Refer to Convergence Diagnostics and Posterior Estimates

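### Table 2.24 judges dose dependence from the intercept of a line through derived dose pairs, but the plan gives no interval for that intercept, and one possible choice of pairs would bias it

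*SAP*

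**What the plan says.** SAP 7.1.2, under Dose Ratio Estimation, describes two ways of forming TIW-QD dose pairs.

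- **Read-off pairs.** For the four TIW doses (10, 15, 25, 30 mg): "Using the observed mean Hgb response values as a bridge, the corresponding QD doses will be estimated using Emax models or a linear model".
- **Selected-response pairs.** Both doses are taken from fitted dose-response models at chosen responses: "The possible Hgb responses choices are: a change of -0.5, -0.25, 0, 0.25, 0.5, 0.75, 1 g/dL between baseline and day 29".

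An additional exploration is then to "draw a TIW dose vs. QD dose plot using the pair of TIW doses and QD doses obtained from the above methods". If the plot looks linear, Dose_TIW = a + b·Dose_QD may be fitted. The decision rule, which also requires approximate linearity, reads: "the magnitude of a dose not deviate from zero in a clinically meaningful way, then it suggests that the dose ratio is not dose dependent". A clinically meaningful a, or a non-linear plot, is taken to suggest possible dose dependence.

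The fit is reported in Table 2.24 (SAP 11.14.6): "Linear Model between the corresponding QD and TIW doses with the same Change in Hemoglobin at Day 29". SAP Table 4 places it in the Stats Analysis column, which the table's notes reserve for formal modelling.

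On uncertainty, the SAP says: "The 95% bootstrap CI of the estimated dose ratios can be constructed based on the 2.5 percentile and the 97.5 percentile of 1000 bootstrap simulations". It also gives Bayesian credible intervals for the ratios. It names no interval method for a or b, no numerical meaning for a clinically meaningful a, and no list of the pairs that enter the fit.

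**The concern.** The points in this regression are not observations. They are calculated from the same two sets of subjects through fitted curves. How far they scatter about the line depends on how the pairs were made, not on how well a and b are known.

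The rule works on the point estimate of a. If a has a large sampling error that is not shown, or is shifted by the fitting direction, a constant ratio can look dose dependent. That matters because the SAP's ED50-ratio and slope-ratio estimates equal the dose ratio only if the ratio is constant, and because the stated purpose is to convert QD regimens to TIW ones.

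**Working it through.** **Inputs.** From Protocol 9.2.1: SD of Hgb change 1 g/dL (1.5 also used in Table 5); TIW linear slope about 0.05 g/dL per mg (0.03-0.07 explored); ratio 2.33, taken as 7/3; E0 = -0.666, Emax = 5.258, QD ED50 = 33.41 mg. From Protocol 4.3: about 15 evaluable per arm. From Protocol 4.5: QD doses 4, 6, 10, 12 mg, to which a placebo arm is added. **Assumption:** QD subjects per arm (PHI113633 excluding Japan) are not given; 15, 30 and 40 were used.

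**1. The plan's nearest figure.** No precision is stated for a or b. Protocol Table 5, for slope 0.05, SDx 10, SDy 1.0 and N = 75, gives 0.020. Recomputed: t(0.975, 73) × √(SDy² − slope²·SDx²) / (SDx·√73) = 1.993 × √0.75 / 85.44 = 0.0202. All 18 rows agree to three decimals.

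**2. Selected-response pairs, two linear fits.** Let the fitted lines be y = α_T + β_T·TIW and y = α_Q + β_Q·QD. Setting them equal gives

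TIW = (α_Q − α_T)/β_T + (β_Q/β_T)·QD.

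All seven points lie exactly on this line, so the regression's residual error and its SEs are zero. The intercept is nevertheless uncertain. To first order, with 15 per TIW arm and 30 per QD arm:

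- Var(α_T) = 1/75 + 16²/8550 = 0.0433
- Var(α_Q) = 1/150 + 6.4²/2736 = 0.0216
- SD(a) ≈ √(0.0433 + 0.0216)/0.05 = 5.1 mg

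Simulation (20,000 runs, true a = 0, true ratio 7/3) gives a little more, because dividing by an estimated slope adds skew:

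- SD of a: 5.8-6.9 mg over 40 down to 15 per QD arm.
- SD of b: 0.74-0.87.
- |a| > 5 mg in 30-39% of trials (QD 15-39 per arm).
- Median b: 2.33-2.34, so no attenuation.
- At TIW slope 0.07 with 30 per QD arm, SD of a is 3.9 mg.

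**3. Selected-response pairs, two Emax fits.** The pairs lie almost on a line.

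- Penalised fits with the SAP priors (1,500 runs): median regression SE 0.035-0.040 mg for a and about 0.005 for b, against sampling SDs of 2.0-2.7 mg and 0.47-0.58. An ordinary 95% interval would cover the truth in only 2-5% of trials. Median b is 2.41-2.49.
- Bayesian fits (2,000 runs, SD taken as known, 39 per QD arm): SE 0.06 mg against SD 2.0 mg for a; 0.01 against 0.44 for b.

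**4. Read-off pairs.** The TIW dose is fixed. The QD dose inherits the error of a 15-subject mean: 1/√15 = 0.258 g/dL, which on a QD slope of 0.05 × 7/3 = 0.1167 is 2.21 mg. This noisy quantity is the regressor. The equivalent QD doses (TIW ÷ 7/3) have mean 8.57 and variance 15.31, so to first order:

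- λ = 15.31/(15.31 + 2.21²) = 0.76
- b = 0.76 × 2.33 ≈ 1.77
- a = 20 − 1.77 × 8.57 ≈ +4.8 mg

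Simulated medians (linear fits):

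| Setting | median b (true 2.33) | median a (true 0) |
|---|---|---|
| SD 1, slope 0.05, QD 15-40 per arm | 1.89 | +3.8 mg |
| SD 1.5, slope 0.05, QD 30 per arm | 1.49 | +7.4 mg |
| SD 1, slope 0.07, QD 30 per arm | 2.09 | +2.1 mg |

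Penalised Emax fits give median b 1.92-1.99; the Bayesian runs gave median a between +3.6 and +4.0 mg. Ordinary regression intervals cover 0.89-0.94 for b and 0.91-0.96 for a at SD 1, so they are imperfect but not void.

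**5. Does the remedy work?** Resampling subjects in both studies and refitting (1,000 bootstraps, selected-response pairs, linear fits) gives coverage of 0.93-0.95 for b and 0.93-0.94 for a. Median interval widths are 2.6-3.1 for b and 21-25 mg for a. For read-off pairs, regressing QD on TIW and inverting gives a median of 2.29-2.36, against 1.84-1.91 in the planned direction in the same runs.

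**The case against.** The best defence is that the SAP never says it will compute, report or act on a regression SE for a or b. Its rule is the clinical size of a, and the mock shell (Linear_TQ) is not in the available text. A reader might infer that the plan treats the pairs as independent data and will publish meaningless errors. The documents do not support that, and the poor coverage above applies only if ordinary intervals were printed.

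A reader might also infer that all pairs come off the same two curves and that the slope is always biased. Neither holds. Read-off pairs use observed TIW arm means and only the QD curve, and attenuation affects only them. The title of Figure 2.18 points to selected-response pairs, where there is no attenuation, although the text of 7.1.2 refers to both methods.

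Finally, the SAP's main check on dose dependence is whether ratios are similar across doses, and those ratios do carry intervals. The line is an additional exploration, no hypothesis is tested, and the conversion decision rests on all approaches together.

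All of this stands and limits the weight of the point. It does not remove it. A rule based on the size of a needs to say how uncertain a is, and with read-off pairs the point estimate itself is shifted.

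**Conclusion.** The point holds in a limited form. Table 2.24 uses a as evidence on dose dependence without an interval for it.

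For selected-response pairs the gap is precision: a varies by about 2 mg (Emax) to 6-7 mg (linear) and b by about 0.4-0.9 when the ratio is truly constant, while the plotted points look almost perfectly linear. For read-off pairs, if fitted, there is also bias: b about 19% low and a about +4 mg at SD 1, or about 1.5 and +7.5 mg at SD 1.5. An intercept of 4 mg is not small beside a lowest TIW dose of 10 mg.

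These sizes rest on the protocol's planning values and on assumed QD arm sizes; the conclusions did not change over 15-40 per arm. They would shrink with a steeper slope. The effect on the final conversion is limited by the exploratory status of the table.

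**What to change.** Amend SAP 7.1.2 and the note to Table 2.24 as follows.

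1. State which pairs, and from which model combinations, enter the fit. Tables 2.11-2.22 could supply 3 × 4 + 9 × 7 = 75. Do not pool read-off and selected-response pairs.
2. Obtain a, b and their 95% intervals by refitting the line in each planned bootstrap replicate or posterior draw, covering both studies. Do not use the regression's own SEs.
3. If read-off pairs are fitted, use Dose_QD = c + d·Dose_TIW, report 1/d as the ratio, and judge c against 0. Resampling alone does not remove the attenuation.
4. State before unblinding what size of intercept would count as clinically meaningful.

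The cost is some SAP wording and a few lines of code inside loops that are already planned. The honest interval for a will be wide, and may show that this display cannot settle dose dependence by itself.
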